Transepical With Transseptal Autologous CD 133+ Bone Marrow Cell Implantation in Patient Following CABG Surgery

ClinicalTrials.gov ID: NCT02870933

Date: February 25th, 2020

Study Protocol

Objectives

Numerous publications in the last decade have been conducted to study the effect of stem cell therapy in improving cardiac function, but the results and the type of cell and implantation procedure vary considerably. The CD133+ bone marrow cell has been shown to possess a high angiogenesis capacity. One previous study published by Nasseri et al. reveals that trans-epicardial implantation of CD133+ for low LVEF patients who underwent CABG showed no significant improvement; nevertheless, it is stated that this result might differ if the trans-septal region is included as a site of stem cell implantation. Therefore, we perform a randomized clinical trial at our Department of Cardiovascular Surgery of National Cardiovascular Center Harapan Kita, Indonesia, and include additional trans-septal implantation of CD133+ to assess the impact of stem cells in improving cardiac function.

Design and Methods

This study was conducted between March 2016 and June 2018, and the study had been approved by the Institutional Review Board and Ethics Committee of National Cardiovascular Centre Harapan Kita (No. LB.02.01/VII/086/KEP.007/2016) and Universitas Indonesia (No:999/UN2.F1/ETIK/XI/2016). This study had also been registered on ClinicalTrial.gov (**NCT02870933**). All patients enrolled in this study had been informed about the procedures and signed the written informed consent. Thirteen patients were randomized and assigned to

each group. Patients in the case group received CABG + implantation of CD133+, and the control group received a CABG-only procedure.

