Inclusion criteria for this study were as follows: i) aged <70, three vessels with coronary artery disease, and indication for coronary artery bypass graft (CABG) surgery; ii) impaired resting global LVEF < 35% with hypoperfused myocardium and abnormal septal wall motion were assessed by cardiac MRI; iii) hypoperfused resting state of LV on MRI. Exclusion criteria were those with i) CAD with valvular disease requiring concomitant valve surgery; ii) acute myocardial infarction; iii) a contraindication for MRI or bone marrow cell (BMC) aspiration procedure; iv) a history of ventricular arrhythmia (\geq Lown III); v) coagulation disorders, including familial hemophilia, sign/symptoms of bleeding disorders, platelets < 80000 mL; vi) chronic obstructive pulmonary disease (COPD); vii) infectious diseases (HIV, Hepatitis B, and HCV); viii) abnormal liver function and renal function test; ix) ventricular conduction disorders; x) electrolyte imbalances; xi) history of immunosuppressant medication, cytotoxic agents, and radiotherapy within four months before date of surgery.

The minimum of 13 patients per group was required to show the inter-group difference in LVEF, with a power (b) of 80% at a two-sided a level of = 0.05. However, 15 patients in each group were included for dropout anticipation.

Bone Marrow (BM) Aspiration

Bone marrow aspiration was done 24 hours before the scheduled CABG. Patients were anesthetized locally, and aspiration was carried out from the posterior iliac crest. A specimen of 190–210 mL of BM volume was harvested and diluted with 25 mL of normal saline containing 40,000U heparin.

CD133+ Separation Process

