The aspirate was then transferred to our stem cell facility. Phosphate buffer saline was added until a total volume of 450 mL was reached and then centrifuged to dispose of the platelet. 1.5 mL of Magnetic MicroBeads[®] anti-CD133 labeling (Miltenyi Biotec) were added and incubated at room temperature for 30 minutes. Separation of the CD133+ was conducted using the *CliniMACS*[®] Magnetic Separation Device (Miltenyi Biotec). The final product was stored at 4–8 °C. The final aspirate volume for implantation was 20 mL, with a CD133+ count ranging from 5–10 million cells. Ten-mL samples were drawn to assess cell numbers, proof of sterility, purity, and the viability of the CD133+ using flow-cytometry FACS Aria III (BD Biosciences). The volume of the initial BM was 190–210 mL. The purity of the CD133+ end-product was 84.4–90.1%, with the viability of 95.2–94.4%.

Surgery

Anesthesia and CABG surgery was carried out according to the regular surgical protocol. The CD133+ was prepared in 20 one-mL syringes with 25G needles (0.5 x 25mm). Trans-septal implantation of CD133+ was performed by going along the left anterior descending artery (LAD). The correct needle placement within the interventricular septum was assessed with the use of trans-oesophageal echocardiography. Each injection of 0.5 mL of CD133+ was administered at injection sites approximately 1.0 cm apart. Ten injections were administered in the trans-septal region, and the other 30 injections were injected along the border area of the hypo-kinetic/hypo-perfused segment, which had been identified by MRI or by visible scarring area and epicardial muscles discoloration.

Cardiac magnetic resonance imaging and analysis

All patients were assessed at the same imaging facility in our hospital before the surgery and six months after the procedure. Our imaging facility was equipped with a Philips Achieva 1.5T

MRI. All subjects underwent resting and stress (adenosine 140 µg/kg/min) MRI with contrast agent *gadopentate dimeglumine* (0.05 mmol/kg). Left ventricular ejection fraction (LVEF), scar size, and wall motion score index (WMSI) were analyzed using *software cvi42*®.

Quality of life and aerobic capacity

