The Minnesota Living with Heart Failure Questionnaire (MLHFQ) and the six-minute walk test (6MWT) were used to evaluate the quality of life and the aerobic capacity before and six months after the procedure. Registered cardiologists assessed the 6MWT for all patients recruited. The Minnesota Living with Heart Failure Questionnaire (MLHFQ) consisted of 21 questions that were used to assess the quality of life.

Statistical Analysis Plan (SAP)

All statistical data were analyzed using *IBM SPSS Statistics version 21.0 (SPSS Inc, Chicago, IL, USA)*. Continuous data were presented as mean \pm standard deviation or median and interquartile range; categorical data were presented as number (n) and percentage. Shapiro-Wilk's test was utilized to assess the distribution of the data. Data were analyzed with independent t-test or Mann Whitney test accordingly. The measurement of scar size proportion presented as improved and non-improved categorical data were compared by the Chi-square test. In all cases, *the P-value* of < 0.05 was considered statistically significant. All of our results were measured by comparing the pre- and post-intervention changes of both groups. Data on boxplot were presented in median and minimum-maximum. Especially, statistical analysis in changes LVEF variable and changes in WMSI used paired t test, analysed defect segment perfusion, MLHFQ and the 6MWT we used Mann-Whitney test and scar size proportion we used chi-square test.

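### Changes are compared between arms without baseline adjustment, and LVEF and WMSI are assigned a paired t test; ANCOVA on the baseline already measured would cure both at almost no cost

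*Combined protocol and SAP*

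**What the plan says.** The Statistical Analysis Plan section gives three statements about how the continuous outcomes are compared.

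- Scale: "All of our results were measured by comparing the pre- and post-intervention changes of both groups".
- General test: "Data were analyzed with independent t-test or Mann Whitney test accordingly", the choice following a Shapiro-Wilk check.
- LVEF and WMSI in particular: "statistical analysis in changes LVEF variable and changes in WMSI used paired t test". Perfusion-defect segments, MLHFQ and 6MWT are assigned Mann-Whitney.

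No regression, ANCOVA or baseline covariate is mentioned in either the protocol or the SAP. The baselines exist: MRI was done "before the surgery and six months after the procedure", and the MLHFQ and 6MWT "were used to evaluate the quality of life and the aerobic capacity before and six months after the procedure".

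The sample-size paragraph under Design and Methods says: "The minimum of 13 patients per group was required to show the inter-group difference in LVEF". The inclusion criteria in the same section require "impaired resting global LVEF < 35" percent, so baseline LVEF is cut off from above.

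Scar size (improved or not, by chi-square) is outside this point.

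**The concern.** There are two linked problems.

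**The named test.** A paired t test compares each patient with himself. Applied within each arm, it asks whether that arm changed. Both arms receive CABG, so a change in the cell arm mixes any surgical effect with any cell effect. Setting one arm's P value beside the other's is not a test of the cells. It also conflicts with the independent t-test named in the same paragraph and with a sample size set for a difference between groups. A reader cannot tell which test produces the LVEF P value.

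**The missing baseline.** A between-arm comparison of changes treats the slope of six-month value on baseline as exactly 1. If the slope is below 1, an arm that starts lower by chance gains more whatever the treatment; if it is above 1, the sign reverses; at 1 there is no bias. With 13 patients per arm, chance differences at baseline are not small. ANCOVA estimates the slope from the data, so it need not be guessed, and the result depends less on which arm happened to start lower.

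**Working it through.** **Inputs.** From the documents: 13 per arm, two-sided 0.05, 80% power. Not given: the LVEF difference, its SD, the baseline-to-follow-up correlation *r*, and the ratio *k* of follow-up SD to baseline SD. So *r* = 0.3–0.8 and *k* = 1–2 are assumptions.

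**1. The plan's 13 per arm.** It cannot be reproduced forwards without a difference and SD. Solved backwards (independent t-test, 24 df, noncentral t), 80% power corresponds to a difference of 1.145 SD of change. That effect is the reference below.

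**2. Chance imbalance.** The SE of the baseline difference is √(2/13) = 0.39 baseline SDs. With imbalance taken as cell minus control, the change-score estimate is off by (slope − 1) × imbalance, where slope = *rk*. Bias is zero when *r* = 1/*k*: *r* = 0.67 at *k* = 1.5, and *r* = 0.5 at *k* = 2.

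**3. Power of ANCOVA.** The variance relative to the change score is k²(1 − r²)/(1 + k² − 2rk), multiplied by 1 + 1/(2n − 4) = 1 + 1/22 for estimating the slope, with 23 df. Example, *k* = 1 and *r* = 0.5: 0.75/1 = 0.75; × 1.045 = 0.784; effect 1.145/√0.784 = 1.29; power 88%.

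| *k* | ANCOVA power, *r* = 0.3 to 0.8 (change score 80%) |
|---|---|
| 1 | 92, 90, 88, 86, 84, 82% |
| 1.25 | 78–87% |
| 1.5 | 78–83% |
| 1.75 | 78–83% |
| 2 | 78–86% |

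At *k* = 1 the confidence interval is 0.83–0.97 times as wide as for the change score. The worst loss in the grid is 1.9 points of power, at or near *r* = 1/*k*, where the two methods differ only by the degree of freedom.

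**4. The LVEF entry limit.** Suppose the limit is what narrows baseline: unselected mean 30–40, SD 10 at both times, *r* 0.5–0.8, truncated at 35.

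- Baseline SD is 5.2–7.0, follow-up SD 7.3–9.3, ratio 1.18–1.74, slope 0.5–0.8.
- ANCOVA power is 79–84%.
- Bias per 1-SE imbalance: smallest (1 − 0.8) × 0.392 × 5.2 = 0.41 LVEF points; largest (1 − 0.5) × 0.392 × 7.0 = 1.37 points.

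**5. Type I error of the change-score t-test** (60,000 simulated trials per setting).

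- Over all randomizations: 0.048–0.052.
- Given a 1-SE baseline difference, equal SDs: 0.047–0.050.
- Given a 2-SE difference, equal SDs: 0.157, 0.130, 0.096, 0.082 at *r* = 0.3, 0.5, 0.7, 0.8.
- Given a 2-SE difference at the same *r*: 0.092, 0.061, 0.050, 0.066 for *k* = 1.5; 0.064, 0.050, 0.072, 0.114 for *k* = 2.
- ANCOVA: 0.048–0.052 throughout.

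An imbalance of 2 SE or more occurs in about 4.6% of trials.

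**6. Paired t tests within arms, no cell effect.** Let *p* be the chance that one arm's paired test is significant (12 df) when both arms share the same true change. Only the cell arm is significant with probability p(1 − p).

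| Shared change (SD of change) | *p* | p(1 − p) |
|---|---|---|
| 0.4 | 0.264 | 0.194 |
| 0.5 | 0.382 | 0.236 |
| 0.6 | 0.512 | 0.250 |
| 0.75 | 0.700 | 0.210 |
| 0.8 | 0.754 | 0.185 |

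Outside that window the figure is lower: about 11% at 0.25 SD and 8% at 1.0 SD. The between-arm change test and ANCOVA stay near 5%.

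**The case against.** The strongest reply is that comparing changes is a valid analysis of a randomized trial and that the paired wording is probably a slip. The same paragraph names the independent t-test and speaks of both groups, so a between-arm test of paired differences may be what was meant. Rewording alone would then settle the contradiction, and ANCOVA would only swap one valid method for another.

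Much of this stands. The literal reading cannot be proved, and the 19–25% figure depends on it and on the chosen window of shared change. The gains of 88–92% need equal SDs and a correlation of 0.5 or less; in the scenario built on the entry limit, ANCOVA is close to neutral. The bias is also modest beside the noise. In that scenario the SE of the change difference is 2.4–3.7 points, so a 1-SE imbalance moves the estimate by about 0.41/2.4 = 0.17 to 1.37/3.7 = 0.37 of one SE. Nothing here quantifies the gain for the three Mann-Whitney outcomes, and a common linear slope is hard to check in 26 patients.

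It does not defeat the point. The contradiction is on the page for the outcome that sized the trial. Where ANCOVA does not gain precision it costs at most about 2 points of power in the assumed range, and it still protects against baseline imbalance. Choosing a rank method where data are skewed is no more data-dependent than the SAP's own Shapiro-Wilk rule.

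**Conclusion.** The point holds, as a change that should be made rather than as a fatal flaw. The plan names incompatible tests for LVEF and WMSI, and it leaves measured baselines unused for all five outcomes. The firm part is textual: a within-arm paired test cannot deliver the between-group LVEF comparison. The benefit of adjustment depends on a correlation and SDs that the documents do not state, so confidence in its size is only medium. It ranges from a material gain in power (equal SDs, low correlation) to none, with protection against chance imbalance whenever the slope differs from 1. Type I error of the change-score test is correct on average and is clearly inflated only in the uncommon trial with an imbalance near 2 SE. The power figures apply to the t-test outcomes, not to those analysed by Mann-Whitney.

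**What to change.** **LVEF and WMSI.** Replace the change-score test and the paired t test wording with ANCOVA of the six-month value on arm and the same variable's baseline. Report the adjusted between-arm difference with its 95% CI.

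**Perfusion-defect segments, MLHFQ and 6MWT.** Use the same ANCOVA for the adjusted difference and CI. Where data are skewed, take the P value from rank ANCOVA; this yields no difference on the outcome scale, so the two should be labelled clearly.

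**All five outcomes.** Use one baseline covariate per outcome, and keep mean or median change by arm as description.

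**Cost.** No new data, one degree of freedom, and at most about 2 points of power under the assumptions above. Since "This study was conducted between March 2016 and June 2018" and the document is dated February 2020, this is a re-analysis. If results had already been seen, it must be labelled post hoc.

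### The SAP names a paired t test for change in LVEF and WMSI, contradicting its own between-group rule and the basis of the sample size

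*Combined protocol and SAP*

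**What the plan says.** The Statistical Analysis Plan section contains a general rule and an endpoint-specific rule.

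- **General rule for continuous data.** After a Shapiro-Wilk check of distribution: "Data were analyzed with independent t-test or Mann Whitney test accordingly". A later sentence adds: "All of our results were measured by comparing the pre- and post-intervention changes of both groups".
- **Endpoint-specific rule (last sentence).** "Especially, statistical analysis in changes LVEF variable and changes in WMSI used paired t test". The same sentence goes on to the remaining outcomes: "analysed defect segment perfusion, MLHFQ and the 6MWT we used Mann-Whitney test and scar size proportion we used chi-square test".

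Outside the SAP, the sample-size paragraph under Design and Methods states: "The minimum of 13 patients per group was required to show the inter-group difference in LVEF". Power is 80% at a two-sided 0.05 level. The number was then raised to 15 per group for dropout. The same section describes two randomized groups, one given CABG plus CD133+ cells, while "the control group received a CABG-only procedure". No matching of patients between groups is described. MRI is done before surgery and at six months.

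**The concern.** A specific instruction is normally taken to override a general one. Read that way, the test for change in LVEF and WMSI is a paired t test. With unmatched arms, the only natural pairing is each patient's two measurements, so the test asks whether the mean change within one arm differs from zero.

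That is not the trial's question. In the cell arm the mean change contains the effect of CABG, the effect of time and any effect of the cells. In the control arm it contains CABG and time. Only the difference between the arms removes what they share. A significant within-arm result in the cell arm, or significance there and not in the control arm, is not evidence that the cells work.

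LVEF is also the only outcome with a sample-size basis. As the SAP stands, it does not settle whether a P-value for LVEF or WMSI produced under it refers to the difference between arms or to change within an arm.

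**Working it through.** **1. The instructions side by side**

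| Place | Instruction | Type of comparison |
|---|---|---|
| SAP, general sentence | Independent t-test or Mann-Whitney | Between groups |
| SAP, sentence on changes | Changes of both groups compared | Between groups, loosely worded |
| SAP, last sentence: LVEF, WMSI | Paired t test | Within one arm |
| SAP, last sentence: perfusion defect, MLHFQ, 6MWT, scar | Mann-Whitney, chi-square | Between groups |
| Design and Methods, sample size | Inter-group difference in LVEF | Between groups |

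One entry disagrees with the others. No sentence ranks them or calls the paired test supplementary.

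**2. The plan's own figure**

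The minimum of 13 per group can be neither reproduced nor refuted, because no LVEF difference or SD is given. Solved backwards for a two-sample comparison at 80% power and two-sided 0.05:

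- Normal approximation: d = (1.960 + 0.842) × √(2/13) = 1.10 SD.
- t test with 24 df (noncentral t): d = 1.145 SD.

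A paired t test in one arm of 13 has 80% power at a mean change of 0.85 SD of the change score. That is a different hypothesis, so the sample-size statement does not support the paired test.

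**3. What a within-arm reading would do if the cells had no effect**

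Assumptions, none of them from the documents: efficacy is claimed from within-arm tests; change scores are normal; both arms change by the same c, in SDs of the change score.

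For one arm of n patients, with T noncentral t on n − 1 df and noncentrality c√n:

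p = P(|T| > t₀.₉₇₅,ₙ₋₁)

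The arms are independent, so the chance of significance in the cell arm and not in the control arm is p(1 − p). Example, n = 13 and c = 0.5: noncentrality 0.5 × √13 = 1.803, critical value 2.179, p = 0.382, and 0.382 × 0.618 = 0.236.

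| c | n=13: cell arm significant | n=13: cell yes, control no | n=15: cell arm significant | n=15: cell yes, control no | Independent t test on change |
|---|---|---|---|---|---|
| 0 | 5% | 5% | 5% | 5% | 5% |
| 0.25 | 13% | 11% | 15% | 13% | 5% |
| 0.5 | 38% | 24% | 44% | 25% | 5% |
| 0.75 | 70% | 21% | 77% | 18% | 5% |
| 1.0 | 91% | 8% | 95% | 5% | 5% |

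Both sizes are shown because the documents give 13 as the minimum and 15 with the dropout allowance. Simulation of 200,000 trials per row at n = 13 agrees: cell arm significant in 0.050, 0.132, 0.383, 0.700 and 0.911, and the independent t test at 0.050 in every row. The last column is constant because c cancels from the difference between arms.

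**4. What it would do if the cells had a real effect**

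Take a true effect of 1.145 SD, which assumes the trial was sized on the change score. The chance of significance in the cell arm and not in the control arm, P(cell significant) × P(control not significant), at n = 13 and control change c = 0 / 0.25 / 0.5 / 0.75 / 1.0, is 92% / 86% / 62% / 30% / 9%. The independent t test has 80% power throughout. The contrast of two within-arm tests can therefore also hide a real effect when the control arm improves.

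**The case against.** The strongest reply is that the word paired is a slip. The last sentence reads like the general rule applied outcome by outcome: a t test for LVEF and WMSI, Mann-Whitney for three others, chi-square for scar size. It already takes the change as the variable analysed, and every other test in it is a between-group test. The sample size agrees. On that view several statements point one way, one word points the other, and the repair is editorial.

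Much of this stands. A slip is quite possible, and so is a supplementary pre/post test. The documents do not show that the between-group test was left out. The error rates in the working depend on a decision rule the SAP does not state and on changes the documents do not give. They illustrate what a within-arm reading can do and do not measure this trial's error rate. The sample-size argument covers LVEF only, not WMSI.

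What does not stand is that nothing need be done. A reader can guess at a slip but cannot confirm it, and the sentence at fault is the one that assigns tests to named outcomes, including the one the trial was sized on. Followed as written, it gives an analysis that cannot answer the trial's question.

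**Conclusion.** The point holds and must be fixed. The contradiction is in the text and depends on no assumed figure: for change in LVEF and WMSI the SAP gives two incompatible instructions, and the more specific one cannot estimate the effect of the cells.

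The size depends on the reading. If efficacy were claimed from the paired test in the cell arm, the chance of a false claim at 13 per arm would run from 5% with no common change, through 38% at 0.5 SD, to 91% at 1 SD. If the claim needed significance in the cell arm and not in the control arm, it would peak at about 24% among the values examined. Both rest on the assumed common change and on a decision rule the SAP does not state. If the wording is a slip or a supplementary test, none of these rates applies and the harm is confined to the ambiguity. Confidence is high that the wording conflicts; no claim is made about which test was actually run.

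**What to change.** In the last sentence of the SAP, replace the paired t test for LVEF and WMSI with an independent t test on change from baseline to six months. This is the smallest change and follows the SAP's own general rule. If the Mann-Whitney branch for non-normal data is meant to apply to these two outcomes, say so in the same sentence. Report the between-group difference with its 95% CI. If paired tests are kept, label them descriptive and base no efficacy claim on them.

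ANCOVA of the six-month value on arm and baseline would also be a valid between-group analysis. It is not in the current SAP, however, so choosing it now should be declared as a departure. Name one analysis and do not leave the choice open.

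The cost is one sentence and, if the paired test was the one run, a rerun in the same software. No new data are needed and the stated minimum of 13 per group is unaffected. The P-value may become less favourable. Because the SAP is written in the past tense, the clarification should be disclosed as made after data collection.
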